7.4 Statistical Analysis of Efficacy Data

The primary efficacy endpoint for this study is the proportion of subjects receiving PTG-100 with clinical remission at Week 12 compared with placebo.

Clinical remission is defined as follows, using the Mayo subscores of stool frequency, rectal bleeding, and endoscopy:

- Stool frequency subscore of 0 or 1 with a pre-specified change of 1 or more from baseline
- Rectal bleeding subscore of 0
- Endoscopy subscore of 0 or 1 (modified so that a score of 1 does not include friability)

The secondary endpoints, all based on comparison of individual PTG-100 dose levels with placebo, include:

1. Proportion of subjects with endoscopic response at Week 12 (Day 84) (defined as an endoscopic subscore of 0 or 1)
2. Proportion of subjects with clinical response at Week 12 (Day 84) (defined as at least 1 point and 30% reduction from baseline in rectal bleeding and stool frequency subscores)
3. Mean change in endoscopy subscore from baseline to Week 12 (Day 84)
4. Mean change in rectal bleeding and stool frequency subscores from baseline to Weeks 2, 4, 6, 8, 10, 12, and 16 (Days 14, 28, 42, 56, 70, 84, and 112)

5. Proportion of subjects with endoscopic remission at Week 12 (Day 84) (defined as an endoscopic subscore of 0)
6. Mean change in complete Mayo Score (including all 4 subscores) from baseline to Week 12 (Day 84)
7. Mean change in partial Mayo Score (excluding endoscopy subscore) from baseline to Weeks 2, 4, 6, 8, 10, 12, and 16 (Days 14, 28, 42, 56, 70, 84, and 112)
8. Mean change in faecal calprotectin levels from baseline to Weeks 6, 12, and 16 (Days 42, 84, and 112)
9. Mean change in IBDQ score from baseline to Week 12 (Day 84)

The exploratory endpoints (all based on comparison of individual PTG 100 dose levels to placebo) include:

1. Mean change in histological score from baseline to Week 12 (Day 84) (assessment tool to be determined)
2. Effects of ADA on PK, safety, and efficacy in subjects with positive ADA

Descriptive statistics will be used to evaluate differences in demographic and baseline characteristics.

For the primary analysis, proportions of subjects with clinical remission will be compared between each dose and placebo using Cochran-Mantel-Haenszel test, with adjustment for stratification factors. Rates of clinical response, endoscopic response, and endoscopic remission will be evaluated similarly.

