Multiplicity will be addressed via closed testing procedure with combined p-values computed for each of the 2 stages of the trial (IA and post-IA). Each stage p-value will be adjusted as appropriate by closed testing multiple comparison approach per Simes.²⁴ This approach controls the overall type 1 error at $\alpha=0.025$, 1-sided.

All analyses will be based on combined Stage 1 and Stage 2 data and include data from the dose(s) that is (are) dropped for Stage 2. Exploratory analyses will be carried out to assess consistency of results between Stages 1 and 2. Analyses of other binary endpoints will be carried out similarly.

Subjects who discontinue prematurely will be considered treatment failures.

Changes from baseline complete Mayo Score, partial Mayo Score, rectal bleeding subscore, stool frequency subscore, endoscopic subscore, IBDQ score, and faecal

calprotectin levels will be analysed using repeated measures mixed analysis of covariance model adjusted for treatment, time point, treatment-by-time point interaction, stratification factors, and baseline values. For subjects who withdraw prematurely, the last observation will be carried forward. These analyses will be based on the Stage 1 and Stage 2 combined data for exploratory purposes.

Details regarding the statistical analyses of efficacy data will be provided in the Statistical Analysis Plan (SAP).

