#### 4.2.4. Adjustments for Covariates

The analyses may be adjusted for the randomization stratification factor, prior treatment with TNF- $\alpha$  antagonist. It will be used in the stratified primary efficacy analysis, and as a covariate in models used for continuous endpoints.

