#### **4.6. Efficacy Evaluations**

##### **4.6.1. Primary Efficacy Analysis**

The primary efficacy endpoint for this study is the proportion of subjects receiving PTG-100 with clinical remission at Week 12 compared with placebo, as defined in Section 2.5.1.

Efficacy analysis for the primary endpoint will be conducted using the FAS population and will be repeated on the PP population as a sensitivity analysis.

The proportion of subjects with clinical remission at Week 12 will be calculated and reported with a two-sided 95% exact confidence interval as an estimate of the true proportion of subjects with clinical remission in the target patient population. Two approaches will be used to report the percentages:

Approach 1: The naïve percentage and associated 95% CI for each dose group, based on data combined across both stages of the trial.

Approach 2: For doses that are selected for Stage 2, the Stage 2-only proportion of subjects with clinical remission and 95% CI will be reported. For doses not selected for Stage 2, the proportions and associated 95% CI based on Stage 1 data only will be reported.

Analysis to examine treatment effect (i.e. odds ratio for clinical remission among subjects with each active dose vs. placebo and 95% CI) will be carried out at the Week 12 time point, employing a Cochran-Mantel-Haenszel test stratified for prior TNF- $\alpha$  use (yes/no). Raw p-values, unadjusted for multiple comparisons, associated with each odds ratio will also be presented.

To obtain the primary endpoint study p-values, Simes-adjusted p-values for each dose regimen vs. placebo that are produced for the primary endpoint from the first and second stages of the study will be combined by using the inverse normal combination function to obtain the final p-value.

The components contributing to the Stage 1 portion of the p-value will include data of subjects from all 4 original dose groups (placebo, low, medium, high dose) who were enrolled during Stage 1, defined as on or before the data snapshot date for the interim look at efficacy.

The components contributing to the Stage 2 portion of the p-value will be data from subjects from the dose groups that were not discontinued who were enrolled after the date of the data snapshot for the interim look at efficacy.

The final p-value for the trial primary endpoint will be a weighted combination of the two components, as described below.

The null hypothesis to be tested is

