$$H_0: \pi_C = \pi_L = \pi_M = \pi_H$$

against the alternative hypothesis

$$H_1: \text{at least one of } \pi_L, \pi_M, \pi_H \text{ is different from } \pi_C$$

where  $\pi_C$  is the response rate for placebo arm, and  $\pi_L, \pi_M, \pi_H$  are the response rates for the three active dose groups. Let  $w_1 = \sqrt{t_1}$  and  $w_2 = \sqrt{1 - t_1}$  be the prespecified weights where  $t_1$  is the statistical information time for interim analysis. Let  $p_{1L}, p_{1M}, p_{1H}$  be the marginal p-values for the three comparisons based on the test statistics of difference of proportions between active dose and placebo group. The test is left tailed. Let  $p_{1(1)} \leq p_{1(2)} \leq p_{1(3)}$  be the ordered p-values. Let  $\tilde{p}_1$  be the Simes adjusted p-value based on the first stage data. Then

$$\tilde{p}_1 = \min\{3p_{1(1)}, \frac{3}{2}p_{1(2)}, p_{1(3)}\}.$$

Let  $p_2$  be the p-value for the comparison for the selected dose versus placebo group. The final combined Simes p-value is given by

$$\Phi(w_1\Phi^{-1}(\tilde{p}_1) + w_2\Phi^{-1}(p_2))$$

where  $\Phi(\cdot)$  is the cumulative distribution function of standard normal variable and  $\Phi^{-1}(\cdot)$  is the inverse cumulative distribution function of standard normal variable.

The final analysis is significant if

$$\Phi(w_1\Phi^{-1}(\tilde{p}_1) + w_2\Phi^{-1}(p_2)) \leq \alpha$$

which is the same as

$$p_2 \leq \Phi \left\{ \frac{\Phi^{-1}(\alpha) - w_1 \Phi^{-1}(\tilde{p}_1)}{w_2} \right\}$$

Analyses of the primary endpoint will be conducted separately for the subjects with prior TNF-alpha use and those without prior TNF-alpha use. Treatment effect estimates will be reported using the naïve odds ratio estimator and its associated 95% CI. P-values will be derived from unstratified Cochran-Mantel-Haenszel tests.

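### The SAP's deciding stage-wise p-values read as a crude difference of proportions, but the protocol's primary test is a CMH test stratified by prior TNF antagonist use

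*SAP*

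**What the plan says.** Protocol 7.4 names one test for the primary endpoint: remission proportions are to be "compared between each dose and placebo using Cochran-Mantel-Haenszel test, with adjustment for stratification factors". The only stratification factor is prior TNF antagonist use. The multiplicity step follows: "Each stage p-value will be adjusted as appropriate by closed testing multiple comparison approach per Simes". No other test is mentioned from which those stage p-values could come.

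SAP 4.6.1 begins the same way. The odds ratio and 95% CI for each dose are obtained "employing a Cochran-Mantel-Haenszel test stratified for prior" TNF-α use, and then "Raw p-values, unadjusted for multiple comparisons, associated with each odds ratio will also be presented".

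The decision rule later in 4.6.1 has a different basis. The three Stage 1 p-values (p1L, p1M, p1H) are called marginal and are "based on the test statistics of difference of proportions between active dose and placebo group". The Stage 2 p-value p2 is said only to "be the p-value for the comparison for the selected dose versus placebo group", with no test named. SAP 4.3 does give a form for p2, inside the same decision inequality: the normal distribution function of the observed Stage 2 difference divided by its standard error. That standard error is built from whole-arm rates and whole-arm counts.

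Two other SAP sections bear on this. Section 4.2.4 says of the randomisation stratum: "It will be used in the stratified primary efficacy analysis". Section 5 states that nothing has changed from the protocol-defined analyses.

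**The concern.** As written, no CMH result enters the criterion that decides the trial. That is a departure from the protocol's primary test, and section 5 does not declare it. It also conflicts with the SAP's own description of the primary analysis as stratified.

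The practical stake is uniqueness. Before unblinding there should be one primary p-value. Here a stratified CMH, a pooled crude difference and an unpooled crude difference can each be defended from the text, and in a borderline trial they can disagree. The ambiguity also spreads: SAP 4.6.2 analyses the binary secondary endpoints in the same way as the primary, and SAP 4.2.5 opens secondary testing only if the primary null hypothesis is rejected.

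**Working it through.** **Candidate statistics, per stage and per dose against placebo**

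- Unpooled crude (the SAP 4.3 form): z = (p_t − p_c) / √[p_t(1−p_t)/n_t + p_c(1−p_c)/n_c]
- Pooled crude: the same numerator over √[p̄(1−p̄)(1/n_t + 1/n_c)]
- Stratified CMH: z = Σ_k(a_k − n_tk·m_k/N_k) / √Σ_k[n_tk·n_ck·m_k(N_k−m_k) / (N_k²(N_k−1))], where k is prior TNF antagonist use yes/no, a_k is remissions on active, m_k is all remissions and N_k is all subjects in the stratum

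**Inputs from the documents.** One-sided α = 0.025. N = 240. Interim at 60 to 80 subjects in four equal arms. Overrun of about 60, counted as Stage 2. True rates (placebo/150/300/900 mg): A = 0.10/0.20/0.31/0.31, B = 0.10/0.17/0.24/0.31, null = 0.10 throughout. At most 50% with prior TNF antagonist use.

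**Assumptions.** 80 subjects at the interim. The two doses with the best observed rates are kept. t1 equals the Stage 1 share of per-arm n. Prior-use share is 30% or 50%. The remission gap, naive minus exposed, is 0 to 15 points (0 to 10 at 30%, where 15 is not feasible). Simes is applied within a closed test at each stage and the stages are combined by inverse normal. CMH has no continuity correction.

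Per-arm sizes for the kept arms are 20 + 15 + (240 − 80 − 60)/3 ≈ 68 with the overrun, and 20 + (240 − 80)/3 ≈ 73 without it.

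**Step 1: the plan's own figures.** The plan states 91% (A), 82% (B) and 2.2% (null) at N = 240. The unpooled crude test gives 91.3–91.5%, 82.9–83.2% and 2.1–2.2% without overrun, and 89.4–89.7%, 80.4–80.8% and 1.9–2.1% with it. With 1,000 runs, the stated figures carry simulation standard errors of √(0.91×0.09/1000) = 0.9, √(0.82×0.18/1000) = 1.2 and √(0.022×0.978/1000) = 0.5 points. The figures are reproduced within that error.

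**Step 2: the three tests compared.** There are 20,000 to 40,000 trials per cell. Ranges run over the assumed shares and gaps.

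| Scenario | Unpooled crude | Pooled crude | Stratified CMH | Unpooled and CMH verdicts differ |
|---|---|---|---|---|
| A, overrun 60 | 89.4–90.0% | 87.8–88.4% | 87.3–89.0% | 1.3–2.2% |
| B, overrun 60 | 80.0–80.7% | 77.6–78.2% | 77.2–79.1% | 1.8–3.1% |
| Null, overrun 60 | 1.7–2.2% | 1.5–1.8% | 1.5–1.7% | 0.2–0.4% |
| A, no overrun | 91.2–91.8% | 89.9–90.5% | 89.5–91.1% | 1.0–1.7% |
| B, no overrun | 82.9–83.1% | 80.6–81.0% | 80.1–81.8% | 1.6–2.8% |
| Null, no overrun | 1.7–2.2% | 1.4–1.9% | 1.6–1.8% | 0.2–0.5% |

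Cell by cell, CMH is 0.7 to 3.1 points below the unpooled test and within 1 point of the pooled test. A further check with 17 + 52 per arm, and arms not balanced within strata, gave the same 1 to 3 points against unpooled and about 1.5 points at most against pooled.

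**Step 3: where the difference comes from.** Much of it is the variance formula rather than the strata. At 0.31 against 0.10 with equal arms, the per-subject variance term is 0.31×0.69 + 0.10×0.90 = 0.304 unpooled and 2×0.205×0.795 = 0.326 pooled. The unpooled z is therefore larger by √(0.326/0.304) − 1 ≈ 3.6%. In scenario A with overrun, a 50% share and no gap, the step from unpooled to pooled costs 89.4 − 87.8 = 1.6 points, and the step from pooled to CMH a further 87.8 − 87.3 = 0.5. With a 15-point gap, CMH recovers to 89.0%, above the pooled 88.4%.

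**The case against.** The strongest reply is that SAP 4.6.1 is loose shorthand. It runs the stratified CMH, takes raw p-values, and the next paragraph Simes-adjusts p-values for each dose. A reader could suppose those are the same p-values, and 4.2.4 would support that. The CMH numerator is itself a weighted sum of within-stratum differences in proportions. The word unstratified is never attached to the stage p-values, 4.6.1 names no test for p2, and the p2 formula in 4.3 sits in a conditional-power derivation meant for futility. At 17 + 52 per arm, Stage 2 carries 52/69 ≈ 75% of the information, so this matters.

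Part of this stands. That the deciding test is crude is an inference: strong for Stage 1, and for Stage 2 resting on 4.3 alone. But the SAP names CMH where it means CMH, including unstratified CMH for the subgroup p-values later in 4.6.1, and the 4.3 formulas contain no stratum. If CMH was intended, the text still has to say so.

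A reader might also infer three stronger things that the documents do not support:

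- **That type 1 error is compromised.** It is not: every test stayed below 2.5% at N = 240.
- **That switching to CMH would bring the reported odds ratio into line with the significance verdict.** It would not. The odds-ratio p-value is raw and pools the stages, while the verdict uses Simes and stage weights. In 100,000 simulated trials per scenario (17 + 52 per arm, best dose kept), the pooled stratified CMH result differed from the final verdict in 5.6–8.4% of trials with CMH stage p-values, and in 4.2–6.9% with the unpooled crude ones.
- **That the stated power proves the crude test was simulated.** The selection rule and t1 are not given, and CMH without overrun (about 90–91% and 80–82%) also lies within the simulation error of the stated figures.

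**Conclusion.** The point holds as an undeclared inconsistency in the primary test. The protocol specifies the stratified CMH, the SAP's decision rule reads as a crude difference, and SAP 4.2.4 and section 5 fit the protocol rather than the rule. The consequence is competing primary p-values, not a loss of error control.

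The size is modest: 1 to 3 points of power against the unpooled form, about 1.5 points at most in either direction against the pooled form, and different verdicts in about 1 to 3% of trials under the two design alternatives. The magnitudes depend on assumed stratum shares, remission gaps, t1 and dose-selection rule, because the documents give no remission rates by stratum and no values for the last two. The textual conflict depends on none of these. It should be resolved before unblinding, and no redesign is needed.

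**What to change.** In SAP 4.6.1, state that p1L, p1M, p1H and p2 are one-sided p-values from the CMH test stratified by prior TNF antagonist use (yes/no), computed separately within each stage, with the direction that favours active treatment made explicit. Rewrite the p2 expression and the conditional-power standard error in 4.3 to match. Keep the crude difference, with its variance form named, as a sensitivity analysis.

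If the crude test is what the sponsor wants, specify pooled or unpooled variance, correct 4.2.4, and declare and justify the change from the protocol in section 5.

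The cost is SAP wording and a few lines of code. The downside of the CMH route is power about 1 to 3 points lower than with the unpooled formula, so the SAP 4.1 power table should be re-run with the CMH version and the planned overrun.

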7 DATA ANALYSES AND SAMPLE SIZE

7.1 Sample Size

Approximately 240 male and non-gravid female subjects aged 18 to 80 with moderate to severe active UC will be randomised. If only 2 arms are selected for continuation following the IA, then up to approximately 210 subjects will be randomised in the study; see [Section 7.2](#).

Prior studies^{1,17-21} suggest treatment effects of approximately 21 percentage point differences from placebo clinical remission rate of approximately 10%. Those values were assumed for purposes of design of this 12-week trial.

The table below shows power for representative scenarios of potential TRUE underlying dose-response relationships, as well as that for no drug effect to assess type 1 error (calculations via Cytel's EAST COMPASS adaptive dose-finding software based on 1000 simulations of each design, with each simulated trial analysed as described in the statistical methods section).²²

TRUE underlying response rates				power (alpha=0.025, 1-sided)			
placebo	150 mg	300 mg	900 mg	N=260	N=240	N=220	N=200
0.1	0.2	0.31	0.31	93%	91%	90%	84%
0.1	0.17	0.24	0.31	83%	82%	78%	75%
0.1	0.1	0.1	0.1	3.4%	2.2%	1.7%	2.1%

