### 2.2. Randomization Methodology

Subjects are randomized 1:1:1:1 by interactive web/voice response system (IXRS) in Stage 1. Subjects will be stratified by prior treatment with TNF- $\alpha$  antagonist use (Yes/ No). Subject enrollment will occur in 2 stages relative to the interim analysis. An independent Data Monitoring Committee (DMC) will monitor safety throughout the study period and may be unblinded as necessary. Limited personnel required for conducting the analyses may also be unblinded to allow necessary safety oversight. The DMC will also be involved in the interim analysis. The purpose of the interim analysis will be to conduct a futility analysis and to identify which treatment arms provide optimal data in order to select those (one or two) PTG-100 dose levels for continual enrollment as the most informative and effective dose arms. Dose selection

will further be made in consideration of safety data and sound clinical judgment, and will be made by the Adaptive Design Review Committee (ADRC), which will be comprised of the DMC and a representative of the Sponsor (not involved in the direct conduct of the study).

After the unblinded interim analysis by the ADRC, additional subjects will be randomized equally (1:1 or 1:1:1 as appropriate) to the selected doses of PTG-100 and placebo with stratification maintained in Stage 2.

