#### 4.2.5. Multiple Comparisons/Multiplicity

Multiplicity will be addressed via a closed testing procedure with combined p-values computed for each of the two stages of the trial (interim analysis and post-interim analysis). Each stage p-value will be adjusted as appropriate by a closed testing multiple comparison approach that controls the overall type 1 error at alpha equal to 0.025, one-sided. Further details will be provided in Section 4.6.

Testing of secondary endpoints will only be performed if the primary efficacy null hypothesis is rejected. A hierarchical testing procedure will be used for the multiple secondary endpoints at the 0.025 (one-sided) alpha level. The first ten secondary endpoints will be tested in the order that they are presented in Section 2.5.1. For secondary endpoints compared at multiple time points, only the comparison at Week 12 will be used for hierarchical testing purposes.

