where  $SE(\hat{\delta}_2) = \sqrt{\frac{\pi_t(1-\pi_t)}{n_{2t}} + \frac{\pi_c(1-\pi_c)}{n_{2c}}}$  and  $n_{2t}, n_{2c}$  are the number of subjects for the active dose and placebo group at the second stage respectively. Since we don't know  $\delta, \pi_t, \pi_c$ , we will replace them by those observed from the first stage data in the conditional power calculation.

PD, efficacy, and safety data will be analyzed to model dose- and exposure-response from Stage 1 of the trial to allow dropping of an ineffective or redundant arm(s). It is also possible that a new dose arm (not tested in Stage 1 of the trial) could be added in Stage 2 for exploratory purposes. Since the trial provides for a 12-week treatment period, it is expected that an additional approximately 60 subjects would be randomized in equal proportions to the 4 treatment groups while the first approximately 60-80 subjects' 12-week data are accumulated and analyzed. Hence, in Stage 2 the remaining subjects would be randomized in equal proportions to the selected dose(s) and placebo. This would yield approximately 70-80 subjects per treatment group for the selected doses. The final analysis will combine all observed data from both Stages 1 and 2.

Dose selection will further be made in consideration of safety data and sound clinical judgment, and will be made by the ADRC), which will be comprised of the DMC and a representative of the Sponsor (not involved in the direct conduct of the study). No pre-specified algorithm will be defined for the IA. Only the ADRC, which will make the dose selection for Stage 2, and the Independent Statistical Center, which will perform the IA, will be unblinded.

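### The only decision rule in SAP 4.6.1 tests the global null and has no two-dose form, so the promised closed test of each dose at one-sided 0.025 is not delivered

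*SAP*

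**What the plan says.** Protocol 7.4 sets up dose-by-dose comparisons: "proportions of subjects with clinical remission will be compared between each dose and placebo using Cochran-Mantel-Haenszel test, with adjustment for stratification factors". On multiplicity it says "Each stage p-value will be adjusted as appropriate by closed testing multiple comparison approach per Simes". SAP 4.2.5 repeats the promise of "a closed testing multiple comparison approach that controls the overall type 1 error at alpha equal to 0.025, one-sided" and leaves the details to Section 4.6.

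The prose of SAP 4.6.1 fits that promise. It speaks of Simes-adjusted p-values "for each dose regimen vs. placebo that are produced for the primary endpoint from the first and second stages of the study", to be combined by the inverse normal function.

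The algebra that follows does not. It states one null hypothesis (placebo and all three doses have equal rates), one Stage 1 Simes p-value over all three doses, and one Stage 2 quantity, p2, said to "be the p-value for the comparison for the selected dose versus placebo group. The final combined Simes p-value is given by" Φ(w1Φ⁻¹(p̃1) + w2Φ⁻¹(p2)). No Stage 2 adjustment is shown. The weights are √t1 and √(1−t1). They are called prespecified, but t1 has no value.

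Two doses may continue. SAP 2.2 says "additional subjects will be randomized equally (1:1 or 1:1:1 as appropriate) to the selected doses of PTG-100 and placebo". Protocol 7.1 says "If only 2 arms are selected for continuation following the IA, then up to approximately 210 subjects will be randomised in the study", so 240 is the size for two doses plus placebo. On how doses are chosen, SAP 4.3 says "No pre-specified algorithm will be defined for the IA".

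**The concern.** A closed test may claim a dose only if every intersection hypothesis containing that dose is rejected: its own, both pairs, and all three. The SAP formula covers only the last. Three things follow.

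- **Two continuing doses.** The formula does not say what to do. Putting each dose through it with its own unadjusted p2 gives two chances at Stage 2 with no correction.
- **One continuing dose.** Significance rejects the statement that no dose works. It does not reject the kept dose's own null. A strong Stage 1 result in a dropped dose makes p̃1 small and lowers the bar for the kept dose.
- **Open weights.** Unless t1 is fixed before the interim look, it could be chosen after Stage 1 is known, and the combination test is then no longer valid.

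Per-dose claims matter here: the protocol compares each dose with placebo and lists choosing regimens as a secondary objective. SAP 4.6.2 also applies the primary method to the dichotomous secondary endpoints and to the pairwise p-values for the continuous ones, so the gap spreads.

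A smaller ambiguity: the formula's p-values come from a difference of proportions, with no word on stratification, while Protocol 7.4, SAP 4.2.4 and the 4.6.1 prose call for a stratified analysis.

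**Working it through.** **Inputs.** Remission is 10% on placebo and 31% on an effective dose (Protocol 7.1, SAP 4.1). Stage 1 has 60 or 80 subjects, or 15 or 20 per arm. About 60 overrun subjects, 15 per arm, count as Stage 2 (SAP 2.1). The total is 240 with two doses continuing and 210 with one.

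Stage 2 per arm, with Stage 1 of 60 / 80:
- Two doses: 15 + (240−60−60)/3 = 55, or 15 + (240−80−60)/3 ≈ 48.
- One dose: 15 + (210−60−60)/2 = 60, or 15 + (210−80−60)/2 = 50.

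Assumed t1 is the Stage 1 share per arm: 15/70 = 0.21 and 20/68 = 0.29 with two doses; 15/75 = 0.20 and 20/70 = 0.29 with one.

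**The plan's own figures.** SAP Table 2 at N=240 gives power of 91% and 82% and type 1 error of 2.2%.
- A full closed test with the best two doses kept, 60 in Stage 1 and no overrun gives 90.7%, 81.6% and 1.7%.
- The formula with one best dose kept, 80 in Stage 1 and 60 overrun gives 90.1%, 81.6% and 2.1%.
- The formula applied to each of two doses without Stage 2 adjustment (no overrun) gives 93.9–94.5%, 87.2–87.8% and 3.5–3.6%, which does not match.

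So Table 2 does not show which rule was simulated. Its type 1 error row covers the global null only and says nothing about per-dose error.

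**A case by hand.** Let Stage 1 p-values be 0.01 and 0.01 in two dropped doses and 0.50 in the kept dose. Then p̃1 = min(3×0.01, 1.5×0.01, 0.50) = 0.015. The largest p2 that is still significant is Φ((−1.96 − w1Φ⁻¹(p))/w2).

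| t1 | SAP formula (p = 0.015) | Kept dose's own combination test (p = 0.50) |
|---|---|---|
| 0.20 | 0.134 | 0.014 |
| 0.25 | 0.156 | 0.012 |
| 0.30 | 0.178 | 0.010 |

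**Simulated false-claim rates**, 200,000 trials per setting, one-sided z-tests, no stratification or dropout. Each cell gives Stage 1 of 60 / 80. The planned rate is 2.5%.

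| Setting, SAP formula applied to each kept dose | Pooled SE | Unpooled SE |
|---|---|---|
| Best one kept (N=210), global null | 2.1% / 2.1% | 2.5% / 2.4% |
| Best two kept (N=240), global null | 3.5% / 3.6% | 4.2% / 4.0% |
| Best two kept (N=240), only 900 mg works | 6.2% / 9.1% | 8.0% / 11.4% |
| Null dose always kept (N=210), one effective dose dropped | 6.0% / 8.8% | 7.6% / 11.4% |
| Null dose always kept (N=210), two effective doses dropped | 8.3% / 12.5% | 10.8% / 16.3% |

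If the best single dose continues and only 900 mg works, the rate is 0.3–0.5%.

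The full closed test gives 1.8–2.6% across the last four rows. The values just above 2.5% arise with the unpooled statistic in these small samples.

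A binding 10% conditional-power stop would not cure the last two rows. With one dropped they become 3.6% / 6.2% pooled and 4.9% / 8.4% unpooled; with two dropped, 5.0% / 8.7% and 7.1% / 11.9%. The SAP's rule is not binding in any case.

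**The case against.** The strongest reply is that the two-dose rates test a rule nobody wrote. The formula speaks of one selected dose, and the prose just before it asks for Simes adjustment in both stages. With Stage 2 Simes read into p2, the two-dose error under the global null falls to 1.9–2.3%. Table 2 points the same way: its null row (3.4%, 2.2%, 1.7%, 2.1%, each from 1000 runs) is 94 rejections in 4000, or 2.35%. If the true rate were 3.5%, a count that low would have probability of about 0.00002, taking the runs as independent. That suggests under-described text and not a plan built on an inflated test.

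This stands as far as it goes. It shows that prose and formula must be reconciled, and that the 3.5–4.2% belongs to the literal formula applied twice. It does not rescue per-dose claims, because Stage 1 still borrows strength from other doses.

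The second reply is that keeping a null dose while dropping effective ones runs against the purpose of the interim analysis, and that Protocol 7.2 promises dose-dropping guidelines in the DMC charter. With only 900 mg effective, a null dose ranks first in just 8–12% of Stage 1 samples. This is fair: the null-dose-kept rates are conditional on an adverse selection and are upper-end values. But selection also weighs safety and clinical judgment, the charter's content is not in these documents, and no algorithm binds the choice. The two-dose failure needs no adverse selection.

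Pooled SE is also the closer stand-in for a CMH test, so the pooled column is the better guide. It still exceeds 2.5% in every failing setting.

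**Conclusion.** The concern holds, and it should be settled before any unblinded interim data are seen. The SAP promises a closed test of each dose and writes down a test of the global null with no two-dose rule and no value for t1.

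With exactly one dose kept, the formula is a valid level-0.025 test of the global null, and if that dose is the best in Stage 1, false claims stay low in the scenarios run. Outside that case the promised control is not assured. With two doses kept and the pooled statistic, the error is 3.5–3.6% under the global null and 6.2–9.1% if only 900 mg works. With a null dose kept it is 6.0–12.5% pooled, as an upper end. The unpooled figures are higher throughout.

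The sizes depend on the assumed t1 of 0.20–0.29, the 10% and 31% rates, and unstratified tests without dropout. The hand example needs no simulation. The unstated stratification of the formula's p-values is an ambiguity and not a demonstrated error.

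**What to change.** Replace the algebra in SAP 4.6.1 with the full closed test:

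1. For each continuing dose s, list every intersection hypothesis containing s: s alone, each pair, and all three.
2. For each intersection, take the Stage 1 Simes p-value over the doses in it and the Stage 2 Simes p-value over the continuing doses in it. Combine the two by the inverse normal function.
3. Claim s only if the largest of these combined p-values is 0.025 or less.
4. State t1 as a number before the interim analysis.
5. State that the stage-wise inputs are one-sided CMH p-values stratified by prior anti-TNF use.
6. Rerun Table 2 for two continuing doses and add partial-null rows (one effective dose, two null).

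The cost is SAP wording, programming and new simulations. With two doses at N=240, power falls 4–7 points from the uncorrected formula: from 93–94% to 88.0–90.1% in the first Table 2 scenario (91% stated), and from 85–87% to 77.8–81.0% in the second (82% stated). The lower ends are with pooled SE, so the stated power may need to be set slightly lower. With one dose at N=210 the loss is 0.5 point or less.
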